Endpoints	
The primary endpoints of the trial are:
 
• The MTD/OBD of BI 905681. The MTD will be assessed based on the number of patients experiencing DLTs, graded according to Common Terminology Criteria for Adverse Events (CTCAE) Version 5.0, in the first cycle of treatment (3 weeks in Schedule A and 4 weeks in Schedule B). The MTD is defined as the highest dose with less than 25% risk of the true DLT rate being equal to or above 33%. Separate MTDs will be determined for Schedule A and Schedule B• Number of patients experiencing adverse events (AEs) during the entire treatment period 
The secondary endpoints of the trial are:
 
• The following PK parameters of BI 905681 will be evaluated after the first administration of BI 905681 (if feasible):
○ C_{max}: maximum measured concentration of BI 905681 in serum after first infusion○ AUC_{0-t_z}: area under the serum concentration-time curve over the time interval from 0 to the last measured time point (t_z)

Safety criteria:	Adverse events (AEs) according to CTCAE Version 5, incidence of DLTs for determination of the MTD/OBD, results of physical examinations, laboratory evaluations, vital signs, and electrocardiograms (ECGs).
Statistical methods:	The trial will be performed as an open-label study. The objective of the design is to determine the MTD of BI 905681 defined as the highest dose with less than 25% risk of the true DLT rate being $\geq 33\%$ (EWOC criterion). The dose-finding in Schedule A and B will be guided by Bayesian 2-parameter logistic regression models with overdose control. Separate MTDs will be determined for Schedule A and Schedule B.

FLOW CHART: BI 905681 (REFMAL 638) SCHEDULE A TRIAL ASSESSMENTS

Schedule A Flow Chart Trial Period	Screening	Treatment Cycles* (1 Cycle = 21 Days)					End of Treatment (EOT)	Follow-up**
Timing	1-28 days prior to first dose	Day 1*** ±72 hrs	Day 2† ±1 day	Day 4**** ±1 day 48-96 hours after dosing	Day 8 ±1 day	Day 15 ±2 days	Within 7 days of EOT decision*****	42-49 days after last dose
Informed consent	X							
Review of in-/exclusion criteria	X							
Demographics and smoking/alcohol history	X							
Medical History	X							
Physical Examination	X	X					X	X
ECOG Performance Status	X	X					X	X
Vital Signs	X	X ^a			X	X	X	X
12 lead-electrocardiogram (ECG) ^b	X	X			X ^b		X	
Safety laboratory blood tests and urinalysis ^c	X	X			X	X	X	X ^d

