4.1.2 Selection of doses in the trial

4.1.2.1 Starting dose for Schedule A

The estimation of the recommended starting dose (RSD) was made on the basis of the ICH Guidance for Industry “S9 Nonclinical Evaluation for Anticancer Pharmaceuticals” ([R11-5034](#)).

Two approaches were taken to calculate the starting dose: (1) use of the HNSTD level determined in the 4-week repeat dose toxicity study in the monkey, the most relevant toxicology species and (2) use of the minimal efficacious dose level determined using an EC₅₀ value from the *in vivo* pharmacology study (Wnt driven breast cancer xenograft model). An approach using the STD₁₀ (a severely toxic dose that causes death or irreversible severe toxicity in 10% of rodents) from the 2-week non-GLP mouse study was not feasible due to morbidity and mortality that was likely a result of anti-drug antibody (ADA) immune complex-related hypersensitivity reactions. The lowest starting dose of 1.0 mg/kg BI 905681 was selected and is expected to be an adequate and safe starting dose.

Approach 1 (use of HNSTD level in the 4-week repeat dose toxicity study in the monkey): The RSD is calculated to be 8.1 mg/kg.

In the 4-week GLP repeat dose toxicity study, the NOAEL was determined to be 150 mg/kg/dose q1w (highest dose tested) and this dose is also considered as the HNSTD based on lack of overt toxicities.

Step 1: Determination of the HNSTD in the repeat dose toxicity study if non-rodent is the most appropriate species (4-week GLP study in the monkey)

Monkey: HNSTD = 150 mg/kg

Step 2: Conversion of 1/6th animal HNSTD to Human Equivalent Dose (HED)

Monkey: 1/6th HNSTD = 25 mg/kg

Conversion factor from monkey dose to HED: 0.324 (based on body surface area scaling factor for the drug molecular weight (43.2 kDa <100 kDa))

HED = 25 mg/kg x 0.324 = 8.1 mg/kg

Approach 2 (use of minimal efficacious dose level determined using an EC₅₀ value from the *in vivo* pharmacology model): The RSD is calculated to be 1.0 mg/kg.

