5.2.5.3 Testing for Cytokine Release

Patients must remain under observation for potential signs and symptoms of cytokine release for at least 6 hours following the end of infusion of BI 905681. If no signs or symptoms are observed during the first three administrations the duration of observation may be reduced to 3 hours for subsequent administrations. For patients who require systemic steroids around the time of administration of BI 905681 or during the post-treatment monitoring period, hospitalisation and monitoring for at least 24 hours is mandatory.

Clinical signs and symptoms of cytokine release will be recorded as AEs. In addition, a panel of cytokines (including, but not limited to IL-2, IL-6, IL-10, IFN- γ , TNF- α , MCP-1) will be measured in peripheral blood in order to monitor release of cytokines after BI 905681 administration. Cytokine measurements will be performed in conjunction with each infusion

at the time points specified in [Appendix 10.2](#).

In addition to the scheduled cytokine measurements, ferritin will be measured at baseline (Cycle 1 Day 1). If a clinically manifested CRS occurs at any time point, unscheduled blood sampling for cytokine and ferritin measurement will be performed, ideally at the start of symptoms (and before start of corticosteroid treatment) and 48-72 hours after the start of symptoms.

Cytokines and ferritin will be measured in a central lab authorised by Boehringer Ingelheim using immunoassay techniques, such as BD Cytometric Bead Array (CBA) and MSD assay. Details are specified in [Appendix 10.2](#), and in the Laboratory Manual.

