In case of clinical symptoms of hepatic injury (icterus, unexplained encephalopathy, unexplained coagulopathy, right upper quadrant abdominal pain, etc.) without lab results (i.e., ALT, AST, total bilirubin) available, the Investigator should make sure these parameters are analysed, if necessary in an unscheduled blood test. Should the results meet the criteria of hepatic injury alert, the procedures described in the Potential DILI checklist should be followed.

Dose Limiting Toxicity

Any medical event fulfilling the criteria of DLT (see [Section 4.1.7](#)) should be reported as an AESI.

Infusion-related Reactions (including Cytokine Release Syndrome)

The following terms describe those events that are to be considered infusion-related reactions. Regardless of grade, these events, when occurring within 72 hours of study drug administration, are considered AESIs and must be reported as such;

- Allergic reaction

Proprietary confidential information © 2019 Boehringer Ingelheim International GmbH or one or more of its affiliated companies

- Anaphylaxis
- Cytokine-release syndrome
- Serum sickness
- Infusion reactions
- Infusion-like reactions
- Any other event which the investigator determines may be a potential infusion-related AE
- Treatment of infusion-related reactions and the handling of subsequent trial dosing are described in [Section 4.1.6.2](#).

The initial clinical sign of a CRS is fever that can rise to high temperatures and is often associated with flu-like symptoms (e.g. nausea, fatigue, headache, myalgias, malaise, chills, rigor, tremor, hypoxia, tachypnea, rash, vomiting, diarrhoea, abdominal pain, muscle and joint pain, and generalised weakness). CRS symptoms may occur quickly during or after administration, or after several hours or days. Patients will be assessed for signs and symptoms of CRS and CRS will be reported as an AESI.

Management guidelines and treatment of CRS are described in [Section 4.1.6.3](#).

Retinal toxicity

Any retinal toxicity (Standardised MedDRA Query ‘Retinal Disorder’) will be reported as an AESI.

Other AESIs

Based on safety observations during the trial, the SMC may define additional AEs as AESIs. If this occurs, investigators will be informed in writing.

Severity of AEs

The severity of AEs should be classified and recorded in the CRF according to the CTCAE v5.0.

Causal relationship of AEs

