### **7.8.1 Adverse Events**

Adverse events will be coded using the Medical Dictionary for Drug Regulatory Activities (MedDRA). Standard BI summary tables and listings will be produced. All adverse events with an onset between start of treatment and end of the residual effect period (REP), a period of 42 days after the last dose of trial medication, will be assigned to the on-treatment period for evaluation.

All treated patients will be included in the safety analysis. In general, safety analyses will be descriptive in nature and will be based on BI standards. No hypothesis testing is planned.

Statistical analysis and reporting of adverse events will concentrate on treatment-emergent adverse events, i.e. all adverse events occurring between start of treatment and end of the residual effect period. Adverse events that start before first drug intake and deteriorate under treatment will also be considered as ‘treatment-emergent.’

The analyses of adverse events (AE) will be descriptive in nature. All analyses of AEs will be based on the number of patients with AEs and not on the number of AEs. Frequency of patients with AEs will be tabulated by treatment dose, highest CTCAE grade, system organ class (SoC) and preferred term after coding according to the current version of MedDRA at the database lock. In addition, AEs will be tabulated by preferred terms only. The SoC will be sorted alphabetically. In tables displaying AEs by preferred terms, this will be sorted by descending frequency of AEs in the “Total” BI 905681 group.

Summary tables and listings of AEs, SAEs, related AEs, related SAEs, AEs of special interest, AEs leading to dose reduction, AEs leading to treatment discontinuation and AEs leading to deaths will be provided.

For the analysis of DLTs with regard to the primary endpoint see [Section 7.4.1](#).

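### The AESI rules for CRS conflict, and serum sickness, allergic reaction and anaphylaxis have only a 72-hour rule, so later non-serious, non-DLT reactions can miss 24-hour reporting and the AESI tables

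*Protocol*

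**What the plan says.** Protocol Section 5.2.6.1 opens its infusion-related reaction entry with a time condition that covers the whole list: "Regardless of grade, these events, when occurring within 72 hours of study drug administration, are considered AESIs and must be reported as such". The list includes allergic reaction, anaphylaxis, CRS and "Serum sickness". It ends with a catch-all for other events that the investigator considers infusion-related, which falls under the same condition.

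The paragraph on CRS that follows says "CRS symptoms may occur quickly during or after administration, or after several hours or days", and then "Patients will be assessed for signs and symptoms of CRS and CRS will be reported as an AESI". Neither sentence mentions 72 hours. Section 5.2.5.3 also treats CRS as possible outside any window: "If a clinically manifested CRS occurs at any time point, unscheduled blood sampling for cytokine and ferritin measurement will be performed".

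In Section 4.1.2.1 the protocol explains that the 2-week mouse study could not be used to set the starting dose because of "morbidity and mortality that was likely a result of anti-drug antibody (ADA) immune complex-related hypersensitivity reactions".

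Section 5.2.6.2 requires AESIs to reach the sponsor within 24 hours, on the same footing as SAEs. SAP Section 7.8.1 promises summary tables and listings of "AEs of special interest". The available SAP text does not say how these events will be identified.

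**The concern.** AESI status decides two things here: whether a non-serious event goes to the sponsor within 24 hours, and whether it appears in the AESI displays. The 72-hour condition applies to reactions of any grade, so the protocol clearly wants low-grade reactions included. Yet the condition is tied to the hours after an infusion, while the section itself describes CRS that can take days to appear. The mechanism suspected in the mouse also depends on anti-drug antibodies.

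For CRS, two sites could classify the same late event differently, and the AESI table would then mix two definitions. For serum sickness, allergic reaction and anaphylaxis there is no second sentence to rely on. In a first-in-human trial of a biologic, mild delayed immune reactions are events one would want counted promptly and in one way.

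**Working it through.** No design figure depends on this point, so the check compares the rules and then applies them to cases.

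**Rules side by side**

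| Event starting after 72 hours | 72-hour list (5.2.6.1) | Separate rule without a time limit | Result |
|---|---|---|---|
| CRS | Not an AESI | CRS sentence in 5.2.6.1: AESI | Contradiction |
| Serum sickness | Not an AESI | None | Not an AESI |
| Allergic reaction, anaphylaxis | Not an AESI | None | Not an AESI |
| Any of these, meeting DLT criteria | Not an AESI | DLT entry in 5.2.6.1, with DLTs recorded throughout the trial (4.1.7): AESI | AESI |
| Any of these, serious | Not an AESI | SAE rule in 5.2.6.2 | Reported within 24 hours as an SAE |

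**Cases**, counting hours from the Day 1 infusion:

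1. Grade 2 CRS, non-serious and not a DLT, starting on Day 5. Elapsed time is 4 × 24 = 96 hours, which exceeds 72. The list excludes it and the CRS sentence includes it.
2. Grade 2 serum sickness, non-serious and not a DLT, starting on Day 10. Elapsed time is 9 × 24 = 216 hours. No rule makes it an AESI. It is an ordinary AE on the eCRF.
3. The same event at Grade 3. Section 4.1.7 classes non-haematologic toxicity of Grade 3 or higher as a DLT, with exceptions that name neither serum sickness nor CRS. It is therefore an AESI unless unequivocally due to the malignancy or an extraneous cause.
4. Case 2 in a patient who has stopped treatment, agrees to contact and declines visits. The vital-status paragraph of Section 5.2.6.2 asks only for deaths or fatal AEs and for treatment-related SAEs and AESIs. Case 2 is none of these, so that paragraph does not require it.
5. Case 2 after the patient's end of trial. Section 5.2.6.2 then asks only for cancer and for treatment-related SAEs and AESIs. For a patient who completes follow-up, end of trial is the visit 42-49 days after the last dose. That is at least 42 × 24 = 1,008 hours, so no event after it can satisfy the 72-hour condition.

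**Time covered by the window.** 72 hours is 3 days. In Schedule A, 3/21 = 14.3% of the interval between doses is inside the window and 18/21 = 85.7% is outside. In Schedule B, which was never opened (SAP Section 4), the figures would have been 3/14 = 21.4% and 11/14 = 78.6%. These are shares of time, not of events. The documents give no distribution of onset times.

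**The case against.** The strongest reply is that little of importance is lost.

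- **Severe events have other routes.** Serious late reactions go in within 24 hours as SAEs, helped by the important-medical-event clause and an always-serious list whose contents are not shown. Late Grade 3 or higher reactions are generally DLTs and so AESIs. The CRS and hypersensitivity stopping rules in Section 3.1.1 carry no time limit. This stands.
- **Decision-makers see Grade 2 events anyway.** Under Section 4.1.3 the Safety Monitoring Committee (SMC) receives all Grade 2 or higher toxicity from the DLT evaluation period at each escalation meeting, with updated safety data beyond it. This stands for Cycle 1 escalation decisions. It replaces neither 24-hour reporting nor a consistent AESI count, and it does not assure Grade 1 events.
- **The SMC may add AESIs.** True, but this is discretionary and follows observations already made.

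A reader might also infer more than the documents support:

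- *That CRS is an AESI only within 72 hours.* It is not excluded, because the later sentence has no limit. Several hours or days also need not mean more than 72 hours.
- *That delayed immune reactions as a class disappear.* Only non-serious, non-DLT events lose AESI status. Outside cases 4 and 5 they remain on the eCRF and in the general AE tables.
- *That the mouse finding proves late onset.* No onset times are given. The window restarts with each dose, so an antibody-driven reaction could follow a later infusion promptly. The monkey, which the protocol calls the most relevant species, showed no adverse findings.
- *That drug still circulating after 72 hours, or a Day 4 visit allowed at "48-96 hours after dosing", shows the window is too short.* Serum concentration does not show when reactions start, and the visit range is a tolerance around a planned 72 hours.

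**Conclusion.** The point holds in a limited form. For CRS, Section 5.2.6.1 contradicts itself. For serum sickness, allergic reaction and anaphylaxis, it sets a 72-hour limit with no alternative rule and no stated reason, despite the hypersensitivity signal in Section 4.1.2.1. What is lost is AESI status, and with it 24-hour reporting and a place in the AESI tables, for reactions that start after 72 hours and are neither serious nor DLTs. In the two situations of cases 4 and 5, the duty to report them is lost as well.

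The size in events cannot be stated. The MTD definition, the DLT rules and the dose-escalation model are not affected. The conclusion assumes that the SAP's AESI displays follow the protocol definition or the sites' flags, since the available SAP text gives no other rule. It is worth correcting because it concerns safety reporting in a first-in-human trial and the correction is cheap.

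**What to change.** Reword the infusion-related reaction entry in Section 5.2.6.1:

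- Reconcile the two CRS statements so that CRS is an AESI whenever it occurs.
- Keep the 72-hour window for acute infusion reactions and infusion-like reactions.
- State that serum sickness, anaphylaxis and allergic reactions considered possibly related to BI 905681 are AESIs whatever the time since dosing. The treatment-related AESI duty in Section 5.2.6.2 then also covers patients who decline visits or are past end of trial.

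Optionally, flag onset within or after 72 hours in the AESI listing already planned in SAP Section 7.8.1, using onset dates already collected. Because the trial was terminated early, the flag is the part still usable for reporting. The protocol wording matters mainly if it is carried into later trials.

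The cost is one reporting paragraph, a few more expedited AESI forms and, if adopted, one extra column in a listing. No dose, schedule or treatment rule changes.

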5.2.6.2 Adverse event collection and reporting

AE Collection

The investigator shall maintain and keep detailed records of all AEs in the patient files. The following must be collected and documented on the appropriate eCRF(s) by the investigator:

- From signing the informed consent onwards until the individual patient's end of trial: all AEs (serious and non-serious) and all AESIs.
- After the individual patient's end of trial: the investigator does not need to actively monitor the patient for AEs but should only report any occurrence of cancer and trial treatment related SAEs and trial treatment related AESIs of which the investigator may become aware of by any means of communication, e.g. phone call. Those AEs should be reported on the BI SAE form (see [Section 5.2.6.2](#)), but not on the eCRF.

Vital Status Data Collection

For patients who discontinue trial medication prematurely and agree to be contacted further but do not agree to physical visits: should be followed up, and from withdrawal from trial treatment until the individual patient's end of the trial the investigator must report all deaths/fatal AEs regardless of relationship, and trial treatment related SAEs and trial treatment related AESIs the investigator becomes aware of.

AE reporting to sponsor and timelines

The investigator must report SAEs, AESIs, and non-serious AEs which are relevant for the reported SAE or AESI, on the BI SAE form via secure e-mail connection or via fax

immediately (within 24 hours) to the [REDACTED]

[REDACTED]:

- Secure email ([REDACTED] SAE mailbox: [REDACTED] or
- Fax ([REDACTED] fax number): [REDACTED]

The same timeline applies if follow-up information becomes available. In specific occasions the Investigator could inform the [REDACTED] upfront via telephone by calling the [REDACTED] phone number ([REDACTED]). This does not replace the requirement to complete and fax the BI SAE form.

With receipt of any further information to these events, a follow-up SAE form has to be provided. For follow-up information the same rules and timeline apply as for initial information. All (S)AEs, including those persisting after individual patient's end of trial must be followed up until they have resolved, have been assessed as "chronic" or "stable", or no further information can be obtained.

Pregnancy

In rare cases, pregnancy might occur in a clinical trial. Once a patient has been enrolled in the clinical trial and has taken trial medication, the investigator must report any drug exposure during pregnancy in a trial participant immediately (within 24 hours) by means of Part A of the Pregnancy Monitoring Form to the sponsor's unique entry point.

Similarly, potential drug exposure during pregnancy must be reported if a partner of a male trial participant becomes pregnant. This requires a written consent of the pregnant partner. Reporting and consenting must be in line with local regulations. The ISF will contain the trial specific information and consent for the pregnant partner.

The outcome of the pregnancy associated with the drug exposure during pregnancy must be followed up and reported to the sponsor's unique entry point on the Pregnancy Monitoring Form for Clinical Trials (Part B).

The ISF will contain the Pregnancy Monitoring Form for Clinical Trials (Part A and B).

As pregnancy itself is not to be reported as an AE, in the absence of an accompanying SAE and/or AESI, only the Pregnancy Monitoring Form for Clinical Trials and not the SAE form is to be completed. If there is an SAE and/or AESI associated with the pregnancy an SAE form must be completed in addition.

Exemptions to SAE reporting

The outcome "disease progression" is used to assess trial endpoints for the analysis of efficacy. It will be recorded on the appropriate page of the eCRF. Only if it meets standard seriousness criteria (see 'Serious adverse event' definition) it will also be recorded on the AE page in the eCRF and on the BI SAE form and SAE reporting process will be followed.

Clinical symptoms and/or signs of PD will be recorded on the AE page in the eCRF. If signs and symptoms of disease progression of the patient's underlying malignancy meet standard

seriousness criteria, they will additionally be reported on the BI SAE form and SAE reporting procedures will be followed.

Exempted events are monitored at appropriate intervals throughout the study at SMC meetings.

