2.1.2 Primary endpoint(s)

[figure not shown]
The primary endpoints of the trial are:

- The MTD/OBD of BI 905681. The MTD will be assessed based on the number of patients experiencing DLTs, graded according to Common Terminology Criteria for Adverse Events (CTCAE) Version 5.0, in the first cycle of treatment (3 weeks in Schedule A and 4 weeks in Schedule B). The MTD is defined as the highest dose with less than 25% risk of the true DLT rate being equal to or above 33%. Separate MTDs will be determined for Schedule A and Schedule B
- Number of patients experiencing adverse events (AEs) during the entire treatment period

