6.2.3.2 Follow-up visit

A follow-up visit should be performed 42-49 days after the last administration of trial medication. The information collected at this visit should include all new AEs that occurred after EOT and a follow-up of AEs ongoing at EOT. Any subsequent anti-cancer therapy administered between EOT and follow-up should be reported.

Wherever possible the follow-up visit must be performed in person, but if the investigator judges appropriate (e.g. in the event the patient is undergoing end-of-life care), follow-up information may be collected by telephone.

The follow-up visit marks the completion of the study for the individual patient. After the completion of the study the patient will receive standard medical care.

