7.3.4 Safety analyses

Adverse events will be coded using the Medical Dictionary for Drug Regulatory Activities (MedDRA). Standard BI summary tables and listings will be produced. All adverse events with an onset between start of treatment and end of the residual effect period (REP), a period of 42 days after the last dose of trial medication, will be assigned to the on-treatment period for evaluation.

All treated patients will be included in the safety analysis. In general, safety analyses will be descriptive in nature and will be based on BI standards. No hypothesis testing is planned.

Statistical analysis and reporting of adverse events will concentrate on treatment-emergent adverse events, i.e. all adverse events occurring between start of treatment and end of the residual effect period. Adverse events that start before first drug intake and deteriorate under treatment will also be considered as 'treatment-emergent.'

Frequency, severity, and causal relationship of adverse events will be tabulated by system organ class and preferred term after coding according to the current version of MedDRA at the database lock.

Laboratory data will be analysed both quantitatively as well as qualitatively. The latter will be done via comparison of laboratory data to their reference ranges. Values outside the reference range as well as values defined as clinically relevant will be summarised. Treatment groups will be compared descriptively with regard to distribution parameters as well as with regard to frequency and percentage of patients with abnormal values or clinically relevant abnormal values.

Vital signs, physical examinations, or other safety-relevant data observed at Screening, baseline, during the course of the trial and at the end-of-trial evaluation will be assessed with regard to possible changes compared to findings before start of treatment.

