**Table 6.1: 1 Dose levels for escalation in Schedule A**

Cohort Dose Level	Proposed dose	Increment from previous dose
1	1.0 mg/kg/q3w	Starting dose
2	2.5 mg/kg/q3w	150%
3	5.0 mg/kg/q3w	100%
4	7.0 mg/kg/q3w	40%
5	8.5 mg/kg/q3w	21.4%

The data will be presented for all dose cohorts separately and in total over all dose cohorts. DLTs occurring during the MTD evaluation period (during the first treatment cycle) will be presented separately.

“Analysing treatment” will be used for reporting of treatment-emergent adverse events (AEs) and to differentiate between screening, on-treatment, and post-treatment safety data. The inequalities start date $\leq$ onset date of the AE $<$  end date of the AE will determine whether the AE will be assigned to the “analysing treatment” or not.

The treatment periods of the trial which will be used for the reporting of AEs and safety laboratory parameters are given in [Table 6.1: 2](#). Safety data recorded during the Residual Effect Period (REP) will be considered as on-treatment. In this trial, the REP is defined as 42 days.

If not specified otherwise, all safety tables will be based on the on-treatment period. AEs that have an onset date during the screening or post-treatment periods will be displayed in separate listings.

**Table 6.1: 2** Definition of treatment periods

Analysing Treatment Period	Start Date (including)	Stop Date (excluding)
Screening	Date of informed consent	The date of first trial medication administration
On-treatment	Date of first administration of trial medication	Date of last trial medication administration + REP*, or death, +1 day whichever comes first, e.g., actual on-treatment period + REP*,
Post-treatment	Last day of on-treatment period +1 day	Date of the last contact date or death, or DBL date, whichever comes first +1 day
MTD evaluation period	Date of first administration of trial medication	Date of first administration of trial medication +21 days

\*Note: A 42-day residual effect period (REP) is defined.

The initial dose of trial medication assigned at the beginning of the first treatment cycle will be used as the label of the analysing treatment.

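### Protocol 5.2.6.2 gives two conflicting rules on which AEs are collected from patients who stop treatment early, accept contact and decline visits, while the analysis treats the 42 days after their last dose as fully observed

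*Protocol*

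**What the plan says.** Protocol 5.2.6.2 states the general rule under AE Collection: "From signing the informed consent onwards until the individual patient's end of trial: all AEs (serious and non-serious) and all AESIs". It names no exception.

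The next paragraph, Vital Status Data Collection, defines a subgroup: "For patients who discontinue trial medication prematurely and agree to be contacted further but do not agree to physical visits". For them, from treatment withdrawal to end of trial, "the investigator must report all deaths/fatal AEs regardless of relationship, and trial treatment related SAEs and trial treatment related AESIs" of which the investigator learns.

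Protocol 6.2.3.2 places the follow-up visit 42 to 49 days after the last dose, makes it the patient's completion of the study, and allows it by telephone where the investigator judges that appropriate. On content: "The information collected at this visit should include all new AEs that occurred after EOT and a follow-up of AEs ongoing at EOT". Footnotes to both flow charts repeat the telephone option.

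On the analysis side, Protocol 2.1.2 lists as a primary endpoint "Number of patients experiencing adverse events (AEs) during the entire treatment period". Protocol 7.3.4 extends the window by a residual effect period (REP), which it describes in these terms: "a period of 42 days after the last dose of trial medication, will be assigned to the on-treatment period for evaluation". SAP 6.1 agrees: "Safety data recorded during the Residual Effect Period (REP) will be considered as on-treatment". SAP 7.8.1 repeats the window, includes all treated patients and counts patients with AEs rather than events. SAP 7 bases percentages on everyone in the set, with or without data. SAP 6.6 imputes only missing baseline laboratory values and refers incomplete AE dates to a sponsor guideline.

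**The concern.** The two paragraphs of 5.2.6.2 ask for different things from the same patients over the same days. A site that takes the Vital Status paragraph as an exception will not collect three kinds of event with onset after withdrawal: non-serious AEs, non-fatal SAEs judged unrelated, and AESIs judged unrelated. A site that follows the general rule will collect them all.

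The analysis does not distinguish these cases. Under a full denominator with no imputation, an AE that nobody asked about enters the tables as no event. The tables at risk are those by dose with preferred term, highest grade, seriousness and relatedness.

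DLTs touch this at one point. They are reported as AESIs (5.2.6.1), and under 4.1.7 a qualifying event is a DLT unless it is clearly due to the malignancy or another outside cause. That is wider than treatment-related, so a late event of doubtful causality could meet the DLT definition and still fall outside the reduced list. SAP 7.4.1 summarises DLTs over the whole treatment period.

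SAP 4 says the trial ends early without an MTD/OBD determination, so the descriptive AE tables carry much of the trial's result.

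**Working it through.** The plan states no figure on this point, so there is none to reproduce. The check compares the texts and then gives illustrative arithmetic.

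**1. Does the reduced rule overlap the analysed period?** It runs from treatment withdrawal to the patient's end of trial, which is the follow-up at day 42 to 49 after the last dose (6.2.3.2). The REP runs to day 42. The reduced rule therefore covers whatever is left of the REP at withdrawal.

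**2. Exception or minimum list?** Everything on the Vital Status list is already required by the AE Collection rule. If that rule still applies in full, the list adds nothing. It has an effect only as an exception, but the text never says so.

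**3. Share of the on-treatment window affected (Schedule A).** Inputs: doses 21 days apart (Protocol, Schedule A flow chart); REP of 42 days and an extra day because the stop date is excluded (SAP Table 6.1: 2); *t*, the days from last dose to withdrawal (assumed).

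- Window after *k* doses = 21(*k* − 1) + 42 + 1 days
- Days under the reduced rule = 42 − *t*

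| Doses | Window (days) | t = 7 | t = 21 |
|---|---|---|---|
| 1 | 43 | 35/43 = 81% | 21/43 = 49% |
| 2 | 64 | 35/64 = 55% | 21/64 = 33% |
| 4 | 106 | 35/106 = 33% | 21/106 = 20% |

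The ceiling is withdrawal on the day of a single dose: 42/43 = 98%.

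**4. Possible undercount for one AE term.** Inputs: N = 30 (Protocol 7.7, per schedule); *m* patients under the reduced rule and *q*, the chance that such a patient has a new, unreported AE of that term (both assumed). Undercount in percentage points = 100·*m*·*q*/30.

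**5. Possible undercount for any AE.** Only a patient with no AE before withdrawal can be missed. With *a* the share who already had one (assumed), multiply by (1 − *a*). Here *q* is the chance of an unreported AE of any kind.

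| m | q | One term | Any AE, a = 0.80 | Any AE, a = 0.95 |
|---|---|---|---|---|
| 1 | 0.1 | 0.3 | 0.07 | 0.02 |
| 3 | 0.3 | 3.0 | 0.6 | 0.15 |
| 6 | 0.5 | 10.0 | 2.0 | 0.5 |

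Within one dose group the steps are coarser. With the minimum cohort of 2 or 3 patients (Protocol 3.1), one patient missed for a given term shifts that rate by 1/2 or 1/3, that is 50 or 33 percentage points. These too are ceilings: the event must occur, be new for that patient and go unreported.

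**The case against.** The strongest reply is that the Vital Status paragraph is a minimum list. It says what must be reported, not that nothing else is collected. Just above it, for the time after end of trial, the authors did write an explicit restriction, so they knew how to limit collection when they meant to. The general rule has no exception, the follow-up contact asks for all new AEs and may be by telephone, Protocol 3.3.4.1 encourages patients who withdraw before progression to return, and SAP 6.6 asks for every effort to complete AE information. On this reading nothing is lost.

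That reply stands far enough that the documents cannot be said to exclude these AEs outright. It does not remove the problem: a list that adds nothing to the general rule invites sites to treat it as an exception, and its limit to related events that come to the investigator's notice resembles the passive rule for the time after end of trial.

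Other parts of the reply also stand. Deaths and related SAEs and AESIs are still reported. The documents offer no support for supposing that patients who decline visits are the sicker ones. Parts of the SAP are redacted, including Section 5.4, which SAP 7.7 cites for on-treatment time, so handling rules may exist that cannot be seen.

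**Conclusion.** The documents contradict themselves on AE collection for this subgroup, and the visible analysis text treats the affected days as observed. If the narrower rule is applied, AE tables by term, grade, seriousness and relatedness are biased downwards. The size cannot be derived, because neither the number of such patients nor their AE risk is given; the figures above rest on assumed *m*, *q*, *a* and *t*.

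Three stronger readings are tempting and not supported:

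- A reader might infer that these patients are counted as free of AEs in the primary endpoint. AEs recorded before withdrawal stay in the data, and a patient with one already counts. In the illustrations the any-AE count moves by 0.02 to 2.0 points out of N = 30.
- A reader might take 98% of the window, or a 33-point shift in a cohort of 3, as the expected effect. Both are ceilings.
- A reader might infer that the MTD is affected. Protocol 7.3.1 and SAP 7.4.1 leave out patients who discontinue in the first cycle for reasons other than a DLT, and the MTD evaluation period ends with that cycle.

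This is a cheap correction worth making, not a flaw that undermines the safety analysis.

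**What to change.** **Protocol 5.2.6.2, Vital Status Data Collection.** State that for patients who agree to be contacted, all AEs (serious or not, related or not) are collected by telephone through 42 days after the last dose, at the day 42 to 49 follow-up contact that 6.2.3.2 already provides. The narrower list then applies only afterwards.

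**SAP 7.8.1, for data already collected under the reduced rule.** Report the number of such patients by dose, list them, and footnote the AE tables to say that their AE collection after withdrawal was limited. As the trial is ending early, this step is useful even if the protocol change comes too late for most patients.

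**Cost.** One protocol paragraph, slightly longer telephone contacts for a few patients and no extra visit; in the SAP, one count, one listing and a footnote.
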